E vs. control groups. However, the sample size in a repeated measures design is reduced when assuming a 1st order autoregressive error covariance structure with rho=0.9 (previous studies range 0.80-0.95). The number of participants per group required to achieve this power is therefore estimated to be n=62; however, this number needs to be adjusted for dropout between randomization and end of study. While the R21 dropout rate was 19.4%, this study will include a longer compensated abstinence period and longer follow-up period, which may increase dropout to 25%. Therefore, **83 participants** will be randomized per group after adjusting for dropout. Secondary Hypothesis 1b: Studies have shown that smokers with larger reductions in CPD may have increased odds of cessation compared to those with smaller reductions. Preliminary analysis from the R21 showed that 52% of participants in Group R-E had achieved a  $\geq 60\%$  reduction in CPD during the 2 weeks leading up to the 1 month follow-up visit relative to the 2 weeks prior to study treatment while only 26% of Group N-RE achieved the same milestone. The randomized sample size of 83 participants per group (62 completers) will provide greater than 80% power ( $\alpha < .05$ ) to detect a similar difference between group R-E relative to each control group. Hypothesis 3: In the R21, cue-elicited craving was measured during post-treatment test sessions at 24-hrs, 2-wks and 1-mo. In the 1-mo test session, differences between R-E and NR-E groups emerged, showing a decrease in cue-elicited craving in Group R-E as compared to Group NR-E ( $d=0.44$ ). In the proposed study, data will be collected at each of the 7 test sessions (over 6-months) and we assume an attenuated effect size (for the same reason noted above for CPD) relative to the R21 findings ( $d=0.40$ ). Given a moderate Rho ( $=0.5$ ), the sample will provide greater than 80% power to detect an effect size of  $d=0.4$  between Group R-E and controls. Thus, the sample size of **83 participants per treatment group (n=166 total)** will provide sufficient power ( $\geq 80\%$ ; and  $\alpha < .05$ ) to detect clinically meaningful smoking efficacy and craving differences for group R-E compared to controls, after accounting for up to 25% dropout.

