**ix. Intervention:** Three intervention sessions will be performed on consecutive days. Participants will arrive at the ABRL/TRAIN lab and compliance with abstinence (breath CO, UDS and breathalyzer) will be assessed. If the participant fails the abstinence assessment, they will be rescheduled; however, if the participant fails the abstinence assessment on the second/third day, they will be permitted to continue in the protocol. This is a departure from the R21, where participants violating the abstinence assessment were discharged from the study. Importantly, the compensation schedule we used to reinforce abstinence resulted in only 10% of the sample being discontinued during treatment. In the present study, we have elected to retain these individuals in the interest of being able to conduct a full intent-to-treat analysis, which we believe is a strength. To discourage multiple violations of abstinence, participants will lose their compensation on the day of the violation but will have the ability to re-earn it by remaining abstinent for the remaining treatment session(s) and the 24-hour test session. Following the abstinence assessment, use of any nicotine products (e.g., e-cigarettes, dip, gum, patch) during the prior 24-hr. period will be assessed. Next, pre-cue measures of craving and physiological reactivity will be obtained as described above for the baseline assessment. After pre-cue measures, individuals in Group R-E will watch the 5-min. video with smoking-related content (same as viewed during baseline cue reactivity) whereas individuals in Group NR-E will view the 5-min. control video with neutral, smoking-irrelevant content. Continuous HR and SC will be collected during the video and the remaining assessments (CQ, MF and BP) will be obtained after. Participants in all three groups will remain seated for 10-min and then Groups R-E and NR-E will be administered a 1-hr of extinction training. As noted above, this 1-hr. training will consist of four sequences of video, picture and in vivo cue exposure. Continuous HR and SC will be collected during the first cue format presented in each sequence and the CQ, MF and BP will be obtained immediately following the last cue format of each sequence (i.e., during a 2-min period where no stimuli are presented). At the completion of exposure training, participants will be asked to sit comfortably for 5-min while the study coordinator removes the HR/SC sensors and the BP cuff. Participants will be reminded that they are being compensated to remain abstinent from smoking and other substance use during the remaining intervention session(s) and/or the 24-hr. test session.

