
**x. Test Sessions:** Participants will complete seven follow-up test sessions: 24-hours, 2-weeks and 1-month, 6-weeks, 2-, 3- and 6-months. We use monetary compensation to minimize test session attrition (only 17.2% of participants did not complete the R21). Consistent with the R21 and Xue et al., 2012, each test sessions will involve a CR assessment identical to the baseline CR assessment described above except that a brief novel smoking picture cue sequence will also be presented. Importantly, some procedural elements will not occur in all test sessions. First, only the 24-hour follow-up test session will be performed under conditions of reinforced abstinence. The goal will be to assess the acute effects of the interventions under the same conditions of abstinence that occurred during the intervention. Participants will be encouraged to maintain their smoking abstinence at the conclusion of this session but will not be compensated for it (participants will be given a referral to the SC state Quitline, a free, anonymous service that supports abstinence). Second, for individuals randomized to the fMRI condition, the 24-hr test session is the only one in which an fMRI session (identical to the one in the baseline assessment) will be performed immediately after the initial CR assessment (cf., Fig. 6); those not assigned to the fMRI condition will remain in the CR laboratory and receive the same CR regimen as administered in the fMRI condition. Third, at the end of all but the 6-mo. test session, participants will receive a smoking diary in which to record the occurrence of both daily smoking and craving. A TLFB assessment of smoking behavior will be performed whenever diary data is not available; all but one of the R21 participants used their diary to collect smoking data as instructed. For those follow-up periods where more than 2-weeks elapse between visits (i.e., period between the 2 and 3 mo. follow-up visit and the period between the 3 and 6 mo. visit), study staff will phone contact participants every 2 weeks to collect diary data. Fourth, in all but the 24-hr. follow-up test session, expired CO and a saliva sample will be collected in order to biochemically corroborate, via CO and cotinine levels, self-report smoking/abstinence (salivary cotinine abstinence cutoff  $\leq$  15 ng/ml per SRNT Guidelines and CO abstinence cutoff  $\leq$  5 ppm). Assessment of the use of any nicotine products (e.g., e-cigarettes, dip, gum, patch) will be assessed at all follow-up visits. At study completion, debriefing will occur in which participant questions will be addressed and recommendations for additional cessation treatment will be provided.

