
**xii. Participant Compensation:** Study retention will be promoted by the following compensation schedule: Clinical assessment = \$30.00; Baseline cue reactivity/fMRI = \$60.00; Intervention sessions 1, 2 & 3 = \$75.00, \$100.00 and \$125.00, respectively; 24-hr. follow-up test session 1 = \$150.00; Test sessions at 2-wks, 1-mo., 6-wks, 2-mo., 3-mo., & 6-mo. = \$100.00. Maximum compensation for participation is \$1,140.00. Retention will also be fostered by frequent phone/text contacts between study staff and participants.

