## 12.0 Data Management

Baseline demographic and clinical measures will be compared across groups using standard statistical methods (e.g., Chi square test of independence for categorical variables; Univariate ANOVA for continuous variables). Characteristics that (i) display imbalance at baseline, (ii) are associated with a dependent measure, or (iii) are known to be predictive of study outcomes (e.g., craving, smoking) will be assessed for inclusion as covariates in the final models. **Primary Aims Analysis:** The primary hypothesis of Aim 1 is that Group R-E will evidence decreased smoking behavior during follow relative to both control groups. Smoking behavior will be measured via smoking diary/TLFB recovered at each visit or by phone, from which, the mean CPD will be calculated between each visit for the period until the last attended visit. Additionally, the smoking diary/TLFB data will be used to compute an indicator of those that achieved a  $\geq$ 60% reduction in CPD relative to baseline smoking at each visit. Generalized linear mixed effects models will be used to analyze the longitudinal smoking behavior data during follow up (using appropriate

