distributions). Overall statistical significance for the effects of treatment group, time, and their interaction will be assessed using a likelihood ratio test that compares the final model to a model consisting of an intercept term alone. The pre-specified hypothesis will be tested using model-based estimates to construct group comparisons across all the planned time points. Normality of residuals will be tested for models where appropriate and when found in error, appropriate transformations or non-parametric methods will be employed. Although mixed effects models have been proven highly efficient in cases where follow up data is missing at random, to accommodate other types of missing data, we will perform analyses using multiple imputation methods (Bayesian approach using both MCMC and FCS). The primary hypothesis associated with Aim 3 is that Group R-E will evidence decreased cue-elicited craving during follow-up testing. General linear mixed effects models will be constructed to assess group differences in craving over time. **Secondary Analysis:** Smoking relapse (i.e., days to 3 consecutive days of smoking ≥5 cigarettes) will be tested using a Cox Proportional Hazards regression model. Log-Log plots of the survival function and inclusion of a time variable treatment term will assess the proportionality assumptions and if models fail this assumption, a stratified Cox Regression model will be used. Also, we will measure end of study 7-day point prevalence abstinence as well as continuous abstinence using smoking diary/TLFB data. The effect of R-E training on abstinence outcomes will be tested using logistic regression models. **Biological Variables:** Exploratory analysis of sex effects on study outcomes will be assessed through main effects and the interaction between sex and study treatment assignment. Where significant interactions are found, sex stratified analyses will be conducted to assess the role of sex in the effect of RET on study outcomes. **Other secondary analyses** will assess i) differences between the control groups on main outcomes, ii) craving and cue reactivity differences during the three intervention sessions, and iii) the effects of treatment on ambient or background craving and cue reactivity (i.e., non-cue-elicited outcomes obtained early in test sessions). All analysis will be conducted using SAS/STAT v. 9.4 and Stata v. 14.

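### The imputation meant to cover data not missing at random itself assumes missing at random, so no planned analysis tests dropout linked to resumed smoking

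*Combined protocol and SAP*

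**What the plan says.** Under Primary Aims Analysis in section 12.0, CPD is derived between visits up to the last visit attended and analysed with generalized linear mixed models. The plan describes these models as efficient when follow-up data are missing at random. In contrast to that case, "to accommodate other types of missing data, we will perform analyses using multiple imputation methods (Bayesian approach using both MCMC and FCS"). It names no imputation model, auxiliary variables, offset, reference-based rule, pattern-mixture model or selection model.

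The same paragraph derives a binary indicator of at least a "60% reduction in CPD relative to baseline smoking at each visit", which falls under the same mixed models and imputation.

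For the secondary outcomes, "we will measure end of study 7-day point prevalence abstinence as well as continuous abstinence using smoking diary/TLFB data", and "The effect of R-E training on abstinence outcomes will be tested using logistic regression models". No rule is given for participants whose abstinence status is missing. The imputation sentence belongs to the primary-aims text and is not extended to these outcomes.

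Three other places bear on this:

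- Section 10.0 iii (Sample Size Estimation): "this study will include a longer compensated abstinence period and longer follow-up period, which may increase dropout to 25" per cent.
- Section 10.0 ix (Intervention): participants who break abstinence on the second or third day are kept "in the interest of being able to conduct a full intent-to-treat analysis".
- Section 10.0 x and xii: "A TLFB assessment of smoking behavior will be performed whenever diary data is not available", there are two-weekly calls in the longer gaps between visits, visits are paid, and "Retention will also be fostered by frequent phone/text contacts between study staff and participants".

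**The concern.** The plan sets up two cases, data missing at random and everything else, and gives the second to a method that covers only the first. In a quit-attempt trial whose outcome is smoking, leaving after resuming smoking is a plausible route out. An intention-to-treat aim makes the unseen outcomes of those who leave part of the question.

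Two things are at stake. First, a reader could take close agreement between the mixed model and the imputation as evidence against informative dropout, although the two share the assumption in doubt. Second, with no rule for abstinence, the analyst could choose between completers only and counting missing as smoking after seeing the data.

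**Working it through.** **The plan's own figures reproduce.** Inputs from section 10.0 iii: d = 0.45, 80% power, alpha 0.05 (two-sided reproduces the figure), six follow-up points, AR(1) with rho = 0.9, 25% dropout.

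- Independent observations: n = 2 × [(1.960 + 0.842)/0.45]² = 77.5, so 78 per group.
- AR(1) factor: (1 + rho)/(T − (T − 2)·rho) = 1.9/2.4 = 0.7917; 77.5 × 0.7917 = 61.4, so 62.
- Dropout: 62/0.75 = 82.7, so 83.

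The sample size is not in dispute. The documents give no CPD standard deviation, so CPD results are in SD units. They use Gaussian outcomes, equally spaced visits and no covariates.

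**Does imputation see what the mixed model misses?** 400 simulated trials, 83 per group, true effect −0.45 SD. A likelihood analysis was compared with Bayesian sequential-regression imputation (10 imputations, arm in the model). In the second and third rows dropout depends on the unseen change in smoking at the missed visit; this mechanism is assumed.

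| Dropout mechanism | Dropout R-E / NR-E | Last visit: truth, likelihood, imputation | Mean of six visits: truth, likelihood, imputation |
|---|---|---|---|
| Missing at random | 17% / 24% | −0.454, −0.453, −0.454 | −0.456, −0.455, −0.456 |
| Unseen rise, both arms | 33% / 33% | −0.450, −0.454, −0.454 | −0.448, −0.449, −0.449 |
| Unseen rise, R-E only | 35% / 23% | −0.446, −0.642, −0.641 | −0.444, −0.550, −0.549 |

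In the last row both methods overstate benefit, by about 0.20 SD at the last visit and 0.11 SD averaged over visits, and they agree with each other.

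**Size of bias at the planned dropout.** Bias = shift × fraction of visit means missing, differenced between arms. If 25% leave uniformly after visits 1 to 5, a dropout misses on average 3 of 6 visits, so 0.25 × 0.5 = 0.125 of visit means are missing.

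- Equal dropout and equal shift: 0.
- Assumed dropout of 25% vs 15%, equal shift: (0.125 − 0.075) × shift = 0.015 SD at a 0.3 SD shift and 0.05 SD at 1 SD.
- Assumed worsening in R-E dropouts only: 0.06 SD at a 0.5 SD shift and 0.125 SD at 1 SD.

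**Tipping point for an observed 0.45 SD, worsening in R-E dropouts only.** Shift = (0.45 − 1.96 × SE)/fraction missing.

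- All leave before follow-up (62 per arm): SE = 0.45/2.802 = 0.161; (0.45 − 1.96 × 0.161)/0.25 = 0.54 SD.
- Dropout spread over visits 1 to 5 (83 per arm): SE 0.1403 (constant effect, GLS) gives 1.40 SD; SE 0.1430 (average of visit means) gives 1.36 SD.
- With Rubin's-rules SEs by simulation (20 imputations, arm-specific models), SE grows from 0.147 at a 1.25 SD shift to 0.148 at 1.4 SD. Then z = (0.45 − 0.125 × shift)/SE = 2.00 and 1.86, crossing 1.96 near 1.3 SD.

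**At least 60% reduction.** Section 10.0 iii gives 52% vs 26%, taken as 32/62 vs 16/62. Counting missing as not achieved, with equal dropout, gives 32/83 vs 16/83. The ratio stays 2.0, the risk difference falls from 25.8 to 19.3 points, and p (uncorrected chi-square) moves from 0.003 to 0.006. Power moves from 85% to 79% (pooled-variance normal approximation).

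**Abstinence.** The documents give no rates. Assume 20% vs 10% among completers (range 10% vs 5% to 30% vs 15%). Counting missing as smoking multiplies each rate by (1 − dropout).

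| Rule | Rates R-E / NR-E | Odds ratio (range) |
|---|---|---|
| Completers only (124 of 166) | 20% / 10% | 2.25 (2.11–2.43) |
| Missing = smoking, 25% dropout each arm | 15% / 7.5% | 2.18 (2.08–2.29) |
| Missing = smoking, R-E 25%, NR-E 15% | 15% / 8.5% | 1.90 (1.83–1.99) |
| Missing = smoking, R-E 15%, NR-E 25% | 17% / 7.5% | 2.53 (2.38–2.70) |

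**The case against.** The strongest reply is that the plan is under-specified rather than wrong. It names two algorithms and no imputation model, and the wording about other types of missing data might mean intermittent gaps or missing covariates. That reading does not fit the contrast drawn with missing at random, and it would still leave informative dropout unexamined. It is true that CO, cotinine or craving in the imputation model could make missing at random more plausible, and a difference from the mixed model would then be informative. The plan does not list such variables, and they would not make the analysis one for data missing not at random.

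On materiality the reply has force. Bias needs arms that differ in dropout or in what follows it, which the documents do not establish. The 25% is a planning ceiling. The simulated one-sided case puts R-E dropout above it and is an illustration, not a forecast. Telephone collection, timeline follow-back, payments and retention of abstinence violators should all limit missing data.

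It is also fair that a Gaussian shift does not carry over directly to a count or log-link model, that the 60% reduction outcome already has a missing-at-random treatment, and that with equal dropout the abstinence rule hardly moves the odds ratio. The intention-to-treat aim argues against a completers-only abstinence analysis, but it does not say which rule replaces it.

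**Conclusion.** The concern holds. As written, the imputation rests on the same assumption as the mixed model and cannot serve the purpose that the plan gives it. No planned analysis examines dropout linked to resumed smoking. That conclusion comes from the text and does not depend on the illustrative figures.

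The size of the consequence cannot be known from the documents. Under the planning values the primary result would be fairly robust unless dropout is early and one-sided. How robust it proves depends on timing and arm pattern that will be known only once the trial has run, which is why the sensitivity analysis should be fixed beforehand. The missing abstinence rule is a real but secondary gap. It matters mainly if dropout differs by arm: with an assumed 10-point difference the odds ratio ranges from 1.90 to 2.53. This should be fixed; it does not invalidate the design.

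**What to change.** Keep the mixed model as primary, and make these changes in section 12.0:

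1. Label the MCMC/FCS imputation as a missing-at-random analysis and list the variables in its imputation model.
2. Pre-specify a delta-adjusted tipping-point analysis for CPD, with shifts varied separately by arm, for example 0 to 1.5 SD in steps of 0.25. State the shifts on the scale of the model finally used. The grid is a suggestion; varying it by arm is essential.
3. State the missing-data rule for the 7-day and continuous abstinence outcomes.
4. Add missing-equals-not-achieved as a sensitivity analysis for abstinence and, optionally, for the 60% reduction outcome.

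Items 1 (the label) and 2 correct what is wrong; the list of imputation variables and item 3 supply missing detail. The cost is analysis-plan wording and modest programming, with no change to sample size, visits or the primary model. The sensitivity estimates may be less favourable. Missing-equals-not-achieved is itself a strong assumption, so unless it is chosen as the abstinence rule it should remain a sensitivity analysis.

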The overarching goal of the proposed study will be to replicate and extend these very encouraging initial findings by 1) increasing the dose of RET (3 vs. 2 sessions) so as to bolster treatment effects, 2) employing fMRI methods to identify patterns of brain activity (BOLD signal changes in regions of interest, ROIs, and functional connectivity) uniquely associated with R-E training and potentially predictive of treatment outcome, and 3) extending follow-up period to more completely assess the long-term effects of RET. Two groups of treatment-seeking smokers will remain abstinent overnight prior to undergoing a baseline cue reactivity assessment and fMRI session (only a portion of each group will undergo fMRI pre- and post-treatment. On their target-quit day, a three-day intervention phase will begin. On each day, Group R-E will receive RET whereas Group NR-E will first be administered retrieval cues that do not contain smoking content (NR) and then receive extinction training (E). The next day, all groups will undergo a cue reactivity assessment and fMRI session identical to baseline. This will end a four-day period of compensated abstinence designed to limit the possibility of reinforcing smoking memories via nicotine administration. Both groups will monitor their smoking behavior and undergo identical laboratory test sessions over a 6-month follow-up period. The aims/hypotheses are:

**Aim 1:** Assess the acute and long-term effects of R-E training on indices of smoking behavior/relapse.

**H1)** Relative to control, Group R-E will show decreased smoking (CPD) during follow-up.

**Secondary H1)** Relative to control, more participants in Group R-E will achieve a 60% smoking reduction (from baseline) during follow-up.

**Aim 2:** Assess RET effects (vs. baseline/control) on fronto-limbic-striatal circuitry function & behavior.

**H2.a)** Cue reactivity: Group R-E will evidence attenuated CR BOLD in medial prefrontal cortex (mPFC: dorsal anterior cingulate-dACC; ventromedial: vmPFC), limbic regions (amygdala, hippocampus) and ventral striatum. Greater reduction in BOLD response in regions of interest will predict decreased smoking.

**H2.b):** Group R-E will evince strengthened resting-state functional connectivity (rsFC) between mPFC regions and ventral striatum (frontostriatal circuits), reduced rsFC between mPFC and amygdala (frontolimbic); and the relative magnitude of change in rsFC will be inversely related to craving and smoking (e.g., CPD).

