
**ii. Participants:** A total of 166 treatment-seeking men and women smokers (83 per group), **aged 25 to 65**, will be enrolled. While we recruited smokers between the age of 21-65 in the R21, we have narrowed the age range in the proposed study in the interest of mitigating concern about the potential confounding effects of brain development in younger participants. Also, since more than 80% of smokers begin smoking before age 21, employment of this age range will ensure, even at the lower bound, that we are recruiting smokers with sufficiently long smoking histories to have well-established smoking-related memories. This age range also ensures the findings will be generalizable to the vast majority of smokers. Additional inclusion requirements are: a) smoke 10+ cigarettes/day for three or more years, b) be willing to make a cessation attempt, c) remain overnight abstinence prior to the baseline smoking cue reactivity assessment, and d) agree to comply with the reinforced abstinence regimen in place during the four laboratory sessions (3 intervention & 1 test). Prospective participants will be excluded if they meet DSM criteria for a psychotic disorder, severe major depression, bipolar affective disorder, substance dependence (other than nicotine) or have a neurological disorder/injury (e.g., dementia, brain tumor, Parkinson's disease, head injury).

**iii. Sample Size Estimation.** A sample of 166 participants assigned equally to 2 treatment groups will provide 80% power to detect clinically relevant reductions in smoking behavior while optimizing power ( $\geq 80\%$ ) to detect meaningful effects across the remaining hypotheses. Hypothesis 1a: In the R21 analysis, a greater reduction in CPD was seen in Group R-E as compared to Group NR-E (**Fig. 2b**: Cohen's  $d=0.5$ ). Since small studies are more likely to report larger effects than larger trials, we have designed this study to have at least 80% power to detect an effect of treatment on CPD with a 10% reduction from that observed in the R21 ( $d=0.45$ ). In the proposed study, we will measure CPD at each of 6 follow-up time points (**Fig. 6**). Under the assumption of independent observations, a total sample size of 78 participants randomized to each group will provide 80% power ( $\alpha < .05$ ) to detect an effect size of  $d=0.45$  between Group R-

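### The relapse fallback is a stratified Cox model with no stratum named: it does not address a treatment effect that changes over time, and on one reading it yields no treatment hazard ratio

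*Combined protocol and SAP*

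**What the plan says.** Section 12.0 (Secondary Analysis) defines relapse as the number of days until a run of three consecutive days at five or more cigarettes. It "will be tested using a Cox Proportional Hazards regression model". Proportionality is examined with log-log survival plots and a second device; the plan continues: "inclusion of a time variable treatment term will assess the proportionality assumptions and if models fail this assumption, a stratified Cox Regression model" will be used. A methods paper on Cox models with non-proportional hazards (reference 112) is cited there. The text names no stratification variable.

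Three other places bear on the question, and none supplies the stratum:

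- Section 10.0, vii stratifies the randomization by gender and by FTND score (5 or below against above 5), but does not link these factors to the relapse model.
- Section 12.0 lets baseline characteristics enter the final models as covariates, without mentioning Cox strata.
- Under Biological Variables, section 12.0 says "Where significant interactions are found, sex stratified analyses will be conducted to assess the role of sex". Those are subgroup analyses triggered by a sex-by-treatment interaction, not by a failed proportionality check.

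The related abstinence outcomes are not time-to-event: "The effect of R-E training on abstinence outcomes will be tested using logistic regression models". Aim 1 in section 1.0 is to "Assess the acute and long-term effects of R-E training on indices of smoking behavior/relapse", but its primary hypothesis is "Relative to control, Group R-E will show decreased smoking (CPD) during follow-up" and its secondary hypothesis is a 60% reduction in smoking.

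**The concern.** The only model term named in the check is treatment by time, so that term asks whether the treatment HR is constant. A stratified Cox model lets the baseline hazard differ freely between strata; it does not let the treatment HR vary with time. The remedy therefore does not match the diagnosis.

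If the check fails, the plan does not say which treatment estimate for relapse will be reported. The analyst would choose the stratum after seeing the data, and one permitted choice reports no treatment effect. No other time-to-relapse treatment contrast is planned to fall back on.

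**Working it through.** **Inputs from the documents.** 83 participants per group (section 10.0, ii), 6 months of follow-up (section 10.0, i), and dropout of up to 25% (section 10.0, iii). The plan states no relapse rate, relapse HR, event count or threshold for the check, so it has no figure of its own to reproduce.

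**Assumptions, all illustrative.** Unless stated otherwise: Weibull control-group relapse (shape 0.6) of 60%, 75% or 90% by day 180; exponential dropout of 25%; one 50/50 baseline covariate multiplying the hazard by g; any change in the treatment HR at day 30.

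**Step 1: treatment as the stratum.** For a relapse in participant i, with treatment indicator z and the risk set limited to the same stratum, the partial-likelihood term is

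exp(b·z_i) / Σ_j exp(b·z_j).

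Within a treatment stratum every z_j equals z_i, so the term is 1/(number at risk) and b disappears. In a simulated trial of 166 the log partial likelihood was −573.093 at b = −1, 0 and 1, with score 0 and information 0. No relapse contributes to a treatment HR.

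**Step 2: a baseline covariate as the stratum, treatment effect truly changing.** The model is h(t | z, s) = h_s(t)·exp(b·z), which still has one constant b. Large-sample results (150,000 per arm; g = 1.5, 3, 15):

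| True HR, before / after day 30 | Early / late HR within strata | Single HR reported by the fallback |
|---|---|---|
| 0.5 / 1.0 | 0.49–0.50 / 0.99–1.01 | 0.59–0.76 |
| 1.0 / 0.5 | 0.99–1.01 / 0.50–0.51 | 0.74–0.91 |

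A separate simulation (40,000 in total, constant control hazard 0.02 per day, true HR 0.5 then 1.5) gave 0.92 unstratified and 0.91 stratified on sex by FTND. The within-stratum HRs were 0.50 early and 1.48 late. Stratifying barely moved the estimate and left the change in effect in place.

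**Step 3: a baseline covariate as the stratum, treatment effect truly constant.** With a constant HR of 0.50, 75% control relapse and the covariate omitted:

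| g | Unstratified early / late HR | Stratified early / late HR |
|---|---|---|
| 1.5 | 0.51 / 0.51 | 0.50 / 0.49–0.50 |
| 3 | 0.52 / 0.57 | 0.50 / 0.49–0.50 |
| 5 | 0.54 / 0.68 | 0.50 / 0.49–0.50 |
| 15 | 0.68 / 0.83 | 0.50 / 0.49–0.50 |

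Here stratification works, provided the covariate is strong and is the one chosen.

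**Step 4: how often the fallback would be used.** 83 per arm, 1,000 to 1,500 trials per scenario, Wald test of treatment × log(time) at an assumed 5% level:

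- Proportional hazards within covariate levels: 3.4–5.1% with no covariate or a 1.5-fold one; 3.4–7.4% with a 3-fold one; 4.7–16.4% with a 15-fold one.
- HR 0.5 and 1.0, in either order: 15.1–31.1% with a covariate up to 3-fold; 7.9–38.7% with a 15-fold one.
- Smaller changes, no covariate: 9–15% for 0.65 and 1.0; 6–9% for 0.6 and 0.8.

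**Step 5: is relapse powered?** By Schoenfeld's formula for 1:1 allocation, d = 4(1.96 + 0.84)² / (ln HR)² ≈ 31.4 / (ln HR)². The assumed scenarios give 80 to 142 relapses. At 80, |ln HR| = √(31.4/80) = 0.63, so HR 0.53; at 142, √(31.4/142) = 0.47, so HR 0.62. Only effects this large would have 80% power.

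**The case against.** The strongest case against concerns weight. Relapse is a secondary analysis. The sample-size section speaks of power this way: "A sample of 166 participants assigned equally to 2 treatment groups will provide 80% power to detect clinically relevant reductions in smoking behavior", and its calculations cover CPD, the 60% reduction and craving, not relapse. The fallback applies only if the check fails, and for moderate changes in effect that is close to the nominal rate (step 4). All of this stands and limits the seriousness.

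Stratifying on treatment is also an unlikely intention, because the plan says relapse will be tested and that model could not test it. Stratifying on a non-proportional covariate is an ordinary reading, and step 3 shows that it can help. That stands too, but it still requires the covariate to be named, and it leaves a changing treatment effect unaddressed.

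Reference 112 may define the stratification. It was not available for this review. The claim is that the plan itself does not state the stratum.

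The documents do not settle how likely a changing effect is. Section 2.0, B describes the earlier study's difference in daily smoking as undiminished, then suggests that it may have been growing in the last two weeks; section 2.0, C repeats the second idea. Both concern cigarettes per day. On relapse itself, section 1.0 reports only a trend towards slower relapse. No failure probability can be drawn from these statements.

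**Conclusion.** The concern holds. The fallback names no stratum. On treatment it removes the treatment HR, which is algebra and needs no assumption. On a baseline covariate it still reports one averaged HR when the effect changes: 0.59–0.76 for a true 0.5 then 1.0, and 0.74–0.91 for the reverse. Those figures rest on the assumed hazards, the assumed change point and 25% dropout, but the constant treatment HR is a property of the model.

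The consequence is limited to one secondary, unpowered analysis in trials where the check fails. The CPD hypothesis and the sample size are untouched. It should be corrected before the data are analysed, but it does not threaten the trial's main result.

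**What to change.** Amend the relapse paragraph of section 12.0 as follows:

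1. The Cox model with treatment as a covariate remains the designated relapse test.
2. Stratification is allowed only on a named baseline covariate that is itself non-proportional (for example gender or FTND category), never on treatment.
3. For non-proportional treatment effects, replace the fallback with one pre-specified treatment contrast, reported whatever the check shows. One choice is the difference in restricted mean relapse-free days to 6 months, with 95% CI and Kaplan-Meier curves. The alternative is period-specific HRs from the treatment-by-time term already planned, with the cut point fixed in advance. The plan should pick one.
4. If the check fails, the Cox HR is described as an average over follow-up.

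The cost is a few sentences and a few lines of code, with no new data. Simulated power if each were used as a test (83 per arm, no covariate effect; control relapse 60 / 75 / 90%):

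| True HR | Cox | Restricted mean | Period-specific, 2 df |
|---|---|---|---|
| 0.65 constant | 50.9 / 59.3 / 68.5% | 49.9 / 57.2 / 68.3% | 40.2 / 48.3 / 57.5% |
| 0.5 then 1.0 | 23.4 / 35.1 / 54.4% | 29.8 / 41.2 / 55.5% | 37.6 / 54.5 / 71.9% |
| 1.0 then 0.5 | 30.4 / 28.7 / 25.7% | 22.5 / 23.7 / 28.7% | 43.9 / 47.1 / 53.1% |

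The restricted mean is within about 2 points of Cox under proportional hazards and 1 to 6 points better for a fading effect. For a delayed effect it ranges from 8 points worse to 3 points better. The period-specific test loses about 11 points under proportional hazards and gains 14 to 27 otherwise, but only because the change was placed at the pre-set cut, which favours it. Since Cox stays the designated test, these differences bear only on the choice of supporting contrast.
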